**Table 4. Dose Modification and Re-treatment Criteria for Oral and IV Study Drugs**

Adverse Event	Severity (CTCAE Grade)	Oral Study Drug (rucaparib)		IV Study Drug (nivolumab)	
		Dose Modification 	Re-treatment	Dose Modification 	Re-treatment

Adverse Event Management Algorithm for a Grade 3 event will be followed (see [Appendix 6](#)). Treatment with IV drug may be resumed if levels return to Grade 2. If total bilirubin elevations > 2 × ULN accompany any of the ALT/AST elevations, IV drug should be discontinued.

Such as, hyper- or hypothyroidism, or glucose intolerance, that resolve or are adequately controlled with physiologic hormone replacement (corticosteroids, thyroid hormones) or glucose-controlling agents, respectively, may not require discontinuation after discussion with and approval from the study medical monitor/designee. Grade 4 drug-related adrenal insufficiency or hypophysitis requires discontinuation regardless of control with hormone replacement.

If any blood parameters remain clinically abnormal > 4 weeks of dose interruption, the patient should be referred to hematologist for further investigations. Bone marrow analysis and/or blood cytogenetic analysis should be considered at this stage according to standard hematological practice.

For patients with Grade 2 ALT or AST elevations with onset after dosing of oral study drug, IV study treatment hold is not required if ALT/AST elevations begin to resolve before the next scheduled infusion and toxicity is considered to be mainly related to oral study treatment. If a subsequent ALT/AST increase of more than 20% is observed following infusion of IV study drug, the next IV study drug administration will be held and, if further increase is observed, the Hepatic Adverse Event Management Algorithm will be followed (see [Appendix 6](#)). In this case, IV study drug should be discontinued if Grade 2 elevations return post re-challenge. If total bilirubin elevations > 2 × ULN accompany any of the ALT/AST elevations, IV drug should be discontinued.

Bilirubin must be within normal limits and alkaline phosphatase must be < 3 x ULN. Monitor liver function tests weekly. If the patient has Grade 3 ALT/AST and continues on oral study drug, and levels do not decline within 2 weeks or they continue to rise, treatment interruption and improvement to ≤ Grade 2 will be required before oral study drug can be resumed, either at the current dose or at a reduced dose.

Monitor liver function tests weekly for 3 weeks after oral study drug has been restarted.

Grade 2 for nivolumab is described as ≥ 1.5 x baseline and baseline is the day the combination treatment starts (ie, Cycle 2 Day 1 in Cohort A1 and A2).

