**Table 4. Dose Modification and Re-treatment Criteria for Oral and IV Study Drugs**

Adverse Event	Severity (CTCAE Grade)	Oral Study Drug (rucaparib)		IV Study Drug (nivolumab)	
		Dose Modification 	Re-treatment	Dose Modification 	Re-treatment
Non-hematological Non-skin AEs					
Adverse event, except fatigue	2	None	N/A	Hold	Grade ≤ 1 or baseline 
Any adverse event (related events lasting > 7 days for nivolumab, exceptions below)	3 or 4	Hold	≤ Grade 2 	Discontinue	
Exceptions with rucaparib					
Alopecia, nausea, vomiting, or diarrhea adequately controlled with systemic antiemetic/antidiarrheal medication administered in standard doses according to the study center routines	3 or 4	None			
ALT/AST provided no signs of liver dysfunction (see laboratory section below)	3	None			
Exceptions with nivolumab					
Uveitis, pneumonitis, bronchospasm, neurological toxicity, myocarditis, hypersensitivity reaction or infusion reaction of any duration	3			Discontinue	
Endocrinopathies, adequately controlled with only physiologic hormone replacement	3			Hold	Grade ≤ 1 or baseline 
Drug-related adrenal insufficiency or hypophysitis	2			Hold	Grade ≤ 1 or baseline 
Adrenal insufficiency regardless of control with hormone replacement	3			Discontinue	
Laboratory abnormalities except as specified below	3			Hold	Grade ≤ 1 or baseline 
Drug-related ALT, AST, or bilirubin	3			Discontinue 	
Adverse event or laboratory abnormality except for those below that do not require delay	4			Discontinue	
Asymptomatic amylase or lipase	4			Hold	Grade ≤ 1 or baseline 

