**Table 4. Dose Modification and Re-treatment Criteria for Oral and IV Study Drugs**

Adverse Event	Severity (CTCAE Grade)	Oral Study Drug (rucaparib)		IV Study Drug (nivolumab)	
		Dose Modification 	Re-treatment	Dose Modification 	Re-treatment
Isolated electrolyte imbalances/abnormalities not associated with clinical sequelae/corrected w/supplementation /appropriate management w/in 72 hours of onset	4			Hold	Grade ≤ 1 or baseline 
Endocrinopathy AEs 	3			Hold	Grade ≤ 1 or baseline 
Non-hematological Toxicity (Skin)					
Adverse event	3	Hold	Grade 2 	Hold	
Hematological Toxicity					
Hematological toxicity (related events lasting >7 days for nivolumab, exceptions below)	3-4	Hold 	Grade 2 	Discontinue	
Confirmed MDS or AML (all new secondary malignancies are Grade 4 per CTCAE 5.0)	4	Discontinue		Discontinue	
Exceptions with nivolumab					
Laboratory abnormalities except as specified below	3			Hold	Grade ≤ 1 or baseline 
Thrombocytopenia > 7 days or associated with bleeding	3			Discontinue	
Laboratory abnormality except for those below that do not require delay	4			Discontinue	
Neutropenia ≤ 7 days	4			Hold	Grade ≤ 1 or baseline 
Lymphopenia or leukopenia	4			Hold	Grade ≤ 1 or baseline 
Laboratory Abnormalities					
Laboratory abnormality	3	Hold	Grade 2 	Hold	
ALT, AST, and/or bilirubin abnormalities	2	None	N/A	Hold 	Grade ≤ 1 or baseline 
ALT/AST elevations	3	None, provided no	N/A	Discontinue 	

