Patients may resume treatment with IV study drug when the drug-related AE(s) improve to Grade ≤ 1 or resolve to baseline value, with the following exceptions which are allowed: Grade 2 fatigue, Grade 2 skin toxicity (if no Grade 3 drug related skin AE). For patients with Grade 2 AST, ALT, or total bilirubin elevations, dosing may resume when laboratory values return to baseline and management with corticosteroids, if needed, is complete. Drug-related pulmonary toxicity, diarrhea or colitis must have resolved to baseline before treatment is resumed. Patients with persistent Grade 1 pneumonitis after completion of a steroid taper over at least 1 month may be eligible for retreatment if discussed with and approved by the study medical monitor. Patients with drug-related endocrinopathies adequately controlled with only physiologic hormone replacement may resume treatment after consultation with the study medical monitor. Adrenal insufficiency requires discontinuation regardless of control with hormone replacement.

The patient may continue at same or reduced dose at the discretion of the investigator. If treatment is resumed at the same dose, and the patient experiences the same toxicity, treatment should be interrupted, then resumed at a reduced dose following improvement of the event to ≤ CTCAE Grade 2. If the patient continues to experience toxicity, additional dose reduction steps are permitted; however, the investigator should consult with the sponsor's medical monitor before reducing to 300 mg BID.

In most cases of Grade 3 ALT or AST elevation, IV study drug will be permanently discontinued. For patients with Grade 3 ALT or AST elevations after the start of IV dosing, but on a background of previous elevations on the first cycle of oral study drug, IV study drug hold is required, but discontinuation is not required, if ALT/AST elevations begin to resolve before the next scheduled infusion, and toxicity is considered to be mainly related to oral study treatment, after the investigator discusses the case with the study medical monitor. Levels will be monitored every 3 days; if they continue to rise more than 20%, the Hepatic

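### Table 4 gives inconsistent nivolumab rules for ALT/AST elevations: only one of two Grade 3 rows leads to the hold exception, and the resumption thresholds do not agree

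*Combined protocol and SAP*

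**What the plan says.** All of this is in Table 4 (Section 5.5), in the nivolumab columns.

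- **Grade 3, first row** (drug-related ALT, AST or bilirubin, under the non-hematological exceptions for nivolumab). The cell reads "Discontinue 5", where the 5 is a footnote mark. The re-treatment cell is blank.
- **Grade 3, second row** (ALT/AST elevations, under laboratory abnormalities). The cell reads "Discontinue 7", where the 7 is a footnote mark. The re-treatment cell is blank.
- **Grade 2 row** ("ALT, AST, and/or bilirubin abnormalities"). Hold, with footnote 8. Re-treatment is at Grade 1 or lower, or baseline, with footnote 3.
- **Footnote 3.** For Grade 2 AST, ALT or total bilirubin elevations, "dosing may resume when laboratory values return to baseline and management with corticosteroids, if needed, is complete".
- **Footnote 5.** "In most cases of Grade 3 ALT or AST elevation, IV study drug will be permanently discontinued". It then describes a case in which a hold replaces discontinuation, and adds: "Treatment with IV drug may be resumed if levels return to Grade 2".
- **Footnote 7.** "If any blood parameters remain clinically abnormal > 4 weeks of dose interruption", then "the patient should be referred to hematologist for further investigations".
- **Footnote 8.** Waives the Grade 2 hold when an ALT/AST elevation that arose after rucaparib dosing is already improving by the next infusion and is attributed mainly to rucaparib.

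**The concern.** A site that meets a liver enzyme elevation has to turn Table 4 into one action: hold or discontinue and, if held, the level at which nivolumab restarts. As printed, the answer depends on which row and which footnote the reader reaches.

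The setting is built into the design. Every patient takes one cycle of rucaparib alone before nivolumab starts (Section 3.1.2), which is the background footnote 5 describes. Section 1.1.2.3.3 lists ALT/AST increase among the most common events of Grade 3 or higher with rucaparib.

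At stake are consistent patient safety management and consistent nivolumab exposure in a trial whose primary endpoint is response to the combination. The tables of adverse events leading to discontinuation and to interruption or delay (Section 9.8.1) are also affected, because the same event could be counted in either.

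**Working it through.** No arithmetic applies, and the plan has no figure to reproduce. The check follows each ALT/AST row to the footnote it cites and compares where a patient ends up.

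**(a) Grade 3: hold or discontinue**

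| Row | Nivolumab action | Footnote | Content of footnote | Route to a hold? |
|---|---|---|---|---|
| Drug-related ALT, AST or bilirubin | Discontinue | 5 | Liver-specific, with a hold exception | Yes |
| ALT/AST elevations (laboratory) | Discontinue | 7 | Blood parameters, hematology referral | No |

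The exception in footnote 5 has four conditions: earlier elevations in the first rucaparib cycle, values starting to fall before the next infusion, attribution mainly to rucaparib, and discussion with the medical monitor. A patient who meets all four is held under the first row and discontinued without exception under the second.

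Footnote 7 does not fit the second row. It presupposes a dose interruption, whereas the cell says discontinue, and it does not mention liver enzymes. Its other use, on the rucaparib hold for hematological toxicity, fits its content.

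**(b) Grade 2: the cell against its own footnote**

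The re-treatment cell accepts either Grade 1 or lower, or baseline. Footnote 3, cited in that cell, names Grade 2 AST, ALT and bilirubin specifically and asks for return to baseline. Take a patient with normal values at baseline who improves from Grade 2 to Grade 1. The cell permits the next dose, and the footnote does not.

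**(c) Resumption at Grade 2 after a Grade 3 event**

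| Source | Level at which nivolumab may resume |
|---|---|
| Footnote 5 (held for Grade 3) | Grade 2 |
| Grade 2 row, re-treatment cell | Grade 1 or lower, or baseline |
| Footnote 3 (Grade 2 liver tests) | Baseline |

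Compare footnotes 5 and 8 first. Elevation during the first rucaparib cycle means onset after rucaparib dosing, which is footnote 8's opening condition. The other two conditions of footnote 8, improvement before the next infusion and attribution mainly to rucaparib, are also in footnote 5. So a footnote 5 patient who has fallen to Grade 2 is in a situation where footnote 8 requires no hold. The two footnotes agree for that patient.

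Two gaps remain. Footnote 3 names Grade 2 fatigue and Grade 2 skin toxicity as the Grade 2 states in which dosing may resume, and it does not mention the footnote 5 case. Also, a patient actually held for Grade 2 must reach Grade 1 or baseline (or baseline only, under footnote 3), while a patient held for Grade 3 under footnote 5 may restart at Grade 2. The less severe event carries the stricter threshold, and no reason is given.

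**The case against.** **Both Grade 3 rows share a default, and the exception can be reached.** Each says discontinue. Footnote 5 speaks of Grade 3 ALT or AST elevation in general, and a drug-related case, the only kind the exception addresses, falls in the row that cites it. This stands against any claim that the exception is out of reach altogether. It does not settle which row governs, because a drug-related elevation is also an ALT/AST elevation and nothing in the laboratory row sends the reader to footnote 5.

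**The 7 may be a misprint or a conversion error.** It may be, and the superscript should be checked against the PDF. Items (b) and (c) do not depend on it.

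**Footnote 3 does not govern the footnote 5 patient.** The Grade 3 re-treatment cells are blank, footnote 3's liver sentence is limited to Grade 2 elevations, and footnote 5 has its own restart clause. This largely stands. What is left is a missing cross-reference and the difference in thresholds. That difference could be deliberate, since a patient held at Grade 2 is one who did not meet footnote 8, but the protocol does not say so.

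**A reader might infer that Grade 2 resumption contradicts a Grade 2 hold outright.** The documents do not support this. The Grade 2 hold is conditional, and footnote 8 lifts it under conditions that a footnote 5 patient meets.

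**A reader might infer that the rule will be used often.** The Section 1.1.2.3.3 statement is for rucaparib alone, and footnote 5 needs four conditions together. The rucaparib-nivolumab data in Section 1.1.4.2 are 8 patients with prostate cancer: one rucaparib reduction for Grade 2 ALT and no related Grade 3/4 events. They started both drugs in the first cycle, so the rucaparib-alone background of footnote 5 could not arise. Nor do they show the event is rare: with 0 of 8, the one-sided 95% upper limit is 1 − 0.05^(1/8) = 0.31.

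**Conclusion.** The concern holds as an internal inconsistency in a live dosing table, in three parts:

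- (a) One of the two Grade 3 ALT/AST rows cites a footnote that does not fit and gives no route to the hold exception.
- (b) The Grade 2 re-treatment cell and its own footnote set different thresholds.
- (c) Footnote 3 does not acknowledge the Grade 2 restart in footnote 5, and a patient held for Grade 2 faces a stricter threshold than one held for Grade 3 under footnote 5.

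Its size is two possible actions for the same Grade 3 patient and three printed resumption thresholds. How many patients would be affected cannot be quantified, because the documents give no rate for these events with the combination in this population. Part (a) assumes that the superscript 7 is in the protocol as issued. The Simon design's stated operating characteristics are unaffected. No view is taken on which action or threshold is right.

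**What to change.** Check the superscript on the Grade 3 ALT/AST laboratory row against the PDF. Then reconcile the two Grade 3 rows, the footnote 7 citation, the Grade 2 re-treatment cell and footnotes 3, 5 and 8 into one consistent statement per grade. Each statement should give the nivolumab action, any exception with its conditions, and the level at which dosing may resume. If different thresholds after Grade 2 and Grade 3 events are intended, say so and cross-refer between footnotes 3 and 5. The sponsor's clinical team decides which rule stands.

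The cost is table and footnote wording in an amendment. The sample size and the planned analyses do not change.

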## 5.5.1 Dose Reduction

### 5.5.1.1 Rucaparib

The dose reduction steps for oral study drug are presented in [Table 5](#).

Dose escalation upon improvement of toxicity to  $\leq$  CTCAE Grade 1 is permitted at the discretion of the investigator.

Dose modifications must be recorded for each patient in the appropriate section of the electronic case report form (eCRF).

**Table 5. Oral Study Drug Dose Reduction Steps**

Starting Dose	600 mg BID
Dose Level: – 1	500 mg BID
Dose Level: – 2	400 mg BID
Dose Level: – 3 a	300 mg BID

a Consult with sponsor's medical monitor before reducing to dose level –3. Further dose reduction may be possible, but requires consultation with the sponsor's medical monitor.

### 5.5.1.2 Nivolumab

There will be no dose reductions permitted for IV study drug.

## 5.6 Management Algorithms for Immuno-oncology Agents

Immuno-oncology (I-O) agents are associated with AEs that can differ in severity and duration than AEs caused by other therapeutic classes. Nivolumab is considered an I-O agent in this protocol. Early recognition and management of AEs associated with I-O agents may mitigate severe toxicity. Management Algorithms have been developed to assist investigators in assessing and managing the following groups of AEs:

- Gastrointestinal
- Renal
- Pulmonary
- Hepatic
- Endocrinopathy
- Skin
- Neurological

The above algorithms are found in [Appendix 6](#) of this protocol.

## 5.7 Treatment of Infusion-related Reactions

Since nivolumab contains only human immunoglobulin protein sequences, they are unlikely to be immunogenic and induce infusion or hypersensitivity reactions. However, if such a reaction were to occur, it might manifest with fever, chills, rigors, headache, rash, pruritus, arthralgias, hypotension, hypertension, bronchospasm, or other allergic-like reactions. All Grade 3 or 4 infusion reactions should be reported within 24 hours to the study medical monitor and reported as an SAE if it meets the criteria. Infusion reactions should be graded according to NCI CTCAE (v5.0) guidelines.

Treatment recommendations are provided below and may be modified based on local treatment standards and guidelines, as appropriate:

**For Grade 1 symptoms:** (mild reaction; infusion interruption not indicated; intervention not indicated):

- Remain at bedside and monitor patient until recovery from symptoms. The following prophylactic premedications are recommended for future infusions: diphenhydramine 50 mg (or equivalent) and/or acetaminophen/paracetamol 325 to 1000 mg at least 30 minutes before additional IV study drug administrations.

**For Grade 2 symptoms:** (moderate reaction required therapy or infusion interruption but responds promptly to symptomatic treatment (eg, antihistamines, non-steroidal anti-inflammatory drugs, narcotics, corticosteroids, bronchodilators, IV fluids); prophylactic medications indicated for  $\geq 24$  hours):

- Stop the study treatment infusion, begin an IV infusion of normal saline, and treat the patient with diphenhydramine 50 mg IV (or equivalent) and/or acetaminophen/paracetamol 325 to 1000 mg; remain at bedside and monitor patient until resolution of symptoms. Corticosteroid and/or bronchodilator therapy may also be administered as appropriate. If the infusion is interrupted, then restart the infusion at 50% of the original infusion rate when symptoms resolve; if no further complications ensue after 30 minutes, the rate may be increased to 100% of the original infusion rate. Monitor patient closely. If symptoms recur, then no further study treatment will be administered at that visit.
- For future infusions, the following prophylactic pre-medications are recommended: diphenhydramine 50 mg (or equivalent) and/or acetaminophen/paracetamol 325 to 1000 mg should be administered at least 30 minutes before IV study drug infusion. If necessary, corticosteroids (up to 25 mg of hydrocortisone or equivalent) may be used

**For Grade 3 or 4 symptoms:** (severe reaction, Grade 3: prolonged [ie, not rapidly responsive to symptomatic medication and/or brief interruption of infusion]; recurrence of symptoms following initial improvement; hospitalization indicated for other clinical sequelae (eg, renal impairment, pulmonary infiltrates). Grade 4: Life--threatening; pressor or ventilatory support indicated):

- Immediately discontinue infusion of study drug. Begin an IV infusion of normal saline and treat the patient as follows: Recommend bronchodilators, epinephrine 0.2 to 1 mg of a 1:1000 solution for subcutaneous administration or 0.1 to 0.25 mg of a 1:10,000 solution injected slowly for IV administration, and/or diphenhydramine 50 mg IV with methylprednisolone 100 mg IV (or equivalent), as needed. Patient should be monitored until the investigator is comfortable that the symptoms will not recur. Study drug will be permanently discontinued. Investigators should follow their institutional guidelines for the treatment of anaphylaxis. Remain at bedside and monitor patient until recovery of the symptoms.

In case of late-occurring hypersensitivity symptoms (eg, appearance of a localized or generalized pruritus within 1 week after treatment), symptomatic treatment may be given (eg, oral antihistamine or corticosteroids).

## **5.8 Treatment Compliance**

### **5.8.1 Rucaparib Treatment Compliance**

Documentation of dosing will be recorded in a study specific dosing diary provided by the sponsor (or designee). Dosing noncompliance is defined as a patient missing > 14 days of medication in a 28-day window for 2 consecutive visits for a nonprotocol-specified reason. The sponsor may require patients meeting noncompliance criteria to discontinue study treatment. Study-site personnel will review dosing information with the patient (or legally authorized representative) on scheduled clinic visit days, providing instructions regarding dose, dose frequency and the number of tablets to be taken for each dose. Patients (or legally authorized representative) will be instructed to keep all unused tablets and containers (empty, partially used, and/or unopened) for accountability at the next scheduled clinic visits. A compliance check and tablet count will be performed by study personnel during clinic visits. Additional details regarding study drug dispensation and return can be found in the pharmacy manual.

Every effort should be made to ensure patients return to the clinic with their study drug containers/unused study drug at the end of each cycle of treatment. Study site personnel should conduct a verbal review of dosing with the patient and document the discussion in the patient's medical record. This may serve as source documentation for the purpose of entering dosing data on the appropriate eCRF.

### **5.8.2 Nivolumab Treatment Compliance**

Each dose of IV study drug will be prepared by a pharmacist or authorized designee and transferred to an infusion set, in accordance with the protocol and applicable local safe handling procedures. The IV infusion will be monitored by the investigator or designee. Treatment compliance will be monitored by drug accountability, and any preparation of infusion deviations (eg, infusion less/greater than 30 min) will be recorded on the patient's eCRF.

## 5.9 Accountability of Protocol-specified Treatment

Study personnel will maintain accurate records of study drug receipt, dispensation, use, return, destruction, and reconciliation for study drugs provided by the sponsor. The IRT system will be used to manage study drug inventory at all sites. In order to function properly, the system will require real-time entry of study drug receipt, dispensation, destruction, etc. by study personnel at the study site.

The site is responsible for the return or destruction of study drug supplied by the sponsor. Authorization to destroy study drug at the site that has not been dispensed to a patient (eg, expired study drug), must be requested from the sponsor prior to destruction. All study drug containers must be accounted for prior to their destruction at the study center, according to institutional procedures for disposal of hazardous materials. Unused and returned study drug product and containers should be destroyed on-site if possible. If destruction on site is not possible, supply should be returned to the drug depot, following the sponsor's instructions.

During the course of the study and at completion of the study, the number of study drug units and containers received, dispensed, returned, and destroyed must be recorded and reconciled. Additional details regarding study drug accountability can be found in the Pharmacy Manual.

